## **6.2 Disposition of Subjects**

The number of subjects included in each analysis population (randomized, ITT, mITT, safety, PP) will be summarized by treatment group. The number of subjects completed, and

discontinued (including the primary reasons for discontinuation) will be summarized for each treatment group.

Subjects who are excluded from an analysis population will be summarized by the primary reasons for exclusion.

### **6.3 Protocol Deviations**

Protocol deviations will not be entered into the database. Deviations leading to exclusion from analysis populations will be identified and summarized.

### **6.4 Data Sets Analyzed**

#### **6.4.1 Randomized Population**

All subjects who are randomized to study treatment will be included in the randomized population and will be analyzed according to the treatment group they were randomized. Listings and summaries will be provided for all randomized subjects.

#### **6.4.2 Intent-to-Treat Population**

All subjects in the randomized population who receive at least one application of study drug and have at least one post-Baseline efficacy assessment will be included in the ITT population and analyzed according to the randomized treatment group. All efficacy analyses will be presented using the ITT population.

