4.3. Reasons for Withdrawal or Termination

If a subject is withdrawn from the study, the subject's enrollment in the study will terminate and study drug application will be discontinued. Efforts will be made to perform all assessments scheduled for the Day 85 Visit prior to subject withdrawal. Subjects may be replaced after consultation with the sponsor.

A subject may be withdrawn from further study participation under the following circumstances:

- At the subject's request.
- Noncompliance with protocol by the subject as determined by the study site staff and investigator.
- Adverse Event (decision to be removed from study made by either the investigator or subject). The investigator must notify the sponsor immediately if a subject is withdrawn because of an AE.

- Decision by the investigator or sponsor that termination is in the subject's best medical interest or administrative decision for a reason other than that of an AE.
- Lost to follow-up, as determined by failure to respond to at least 2 telephone calls followed by certified letter sent to the subject's last known address. All attempts to contact the subject must be documented in the subject's source documents.
- Sponsor decision to halt the entire study.

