6.3.8. Early Termination Visit

If a subject terminates the study early for reasons other than an AE, attempts will be made to complete the assessments required for the Day 85 Visit.

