9.3. Description of Statistical Methods

9.3.1. General Approach

This study will be evaluated using 3 analysis sets: intent-to-treat (ITT), per protocol (PP), and safety. Efficacy conclusions will be drawn from the ITT analysis set. The ITT analysis set will consist of all randomized subjects with at least one post-baseline efficacy assessment and will be based on randomized study group, regardless of study drug received. The PP analysis set will be used to support the efficacy findings in the ITT analyses and will include subjects with no major protocol deviations. Safety conclusions will be drawn from the safety analysis set. The safety analysis set will include all subjects that received at least one application of study drug and had at least one post-baseline safety assessment with treatment based on study drug received regardless of randomization group.

Demographics will be summarized using the safety analysis set by baseline age, gender, race, ethnicity, height, and weight. The primary efficacy analysis will be conducted on the ITT population. For continuous variables, the mean, standard deviation (SD), median, and range will be presented along with the 95% confidence interval (CI). Categorical variables will be summarized by proportions along with the 95% CI.

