## **6. STATISTICAL AND ANALYTICAL PLANS**

### **6.1 General Methodology**

All statistical processing will be performed using SAS® 9.4 or higher. No interim analyses are planned. This Phase 2 study is designed to identify the response of BTX 1204 4.0% BID compared to Vehicle BID. Statistical tests will be exploratory. No adjustments for Type I error will occur.

Descriptive statistics will be used to provide an overview of the efficacy and safety results. For categorical parameters, the number and percentage of subjects in each category will be presented. For continuous parameters, descriptive statistics will include n (number of subjects), mean, standard deviation (SD), median, minimum and maximum.

The primary method of handling missing efficacy data in the Intent-to-Treat (ITT) and modified Intent-to-Treat (mITT) analysis sets will be based on last observation carried forward (LOCF). Repeated measures analyses will be used on the observed data as a sensitivity analysis on the primary endpoint.

The efficacy analysis performed on the ITT population is considered the primary analysis. The efficacy analyses performed on the mITT and per-protocol (PP) populations are considered supportive analyses.

The number of subjects in each analysis set will be summarized. Reasons for study withdrawal during the study will be summarized using frequencies and percentages by treatment group.

Reported AEs, medical history terms and prior and concomitant procedures and therapies will be classified on the basis of Medical Dictionary for Regulatory Activities (MedDRA) terminology. Prior and concomitant medications will be classified on the basis of World Health Organization Drug Dictionary (WHO-DDE) terminology.

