**Analysis Windows for Efficacy and Safety Assessments**

Scheduled Visit	Target Study Day	Window (Days)
Day 15	15	9 to 21
Day 29	29	22 to 42
Day 57	57	43 to 70
Day 85	85	71 to 98

Data collected at early termination and unscheduled visits prior to study day 9 will not be analyzed, with the exception of those identified as Baseline values. Efficacy and safety data collected at early termination and unscheduled visits after study day 98 will not be included in analyses.

The definition for the study day included in each study window is defined as below:

Study Day prior to Day 1 = Visit Date – Day 1 Date

Study Day on or after Day 1 = Visit Date – Day 1 Date + 1

If an assessment's mapped visit is a visit at which the subject has data from a scheduled visit present, or if no analyses are planned for the assessment at the mapped visit, the data collected at the early termination or unscheduled visit will not be included in analyses.

In the event of multiple values from unscheduled or early termination assessments within an analysis window, the value closest to the scheduled visit target study day will be used for analyses. If two values tie as closest to the time point (for example, one value is before and the other value is after the time point), then the later value will be selected.

Data collected at all visits will be included in the data listings with visit presented as reported by the site.

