#### **6.1.5 Handling of Dropouts or Missing Data**

All efforts will be made to minimize the occurrence of missing data. It is not expected that dropout rates will differ between groups. Therefore, the primary method of handling missing efficacy data in the ITT and mITT analysis set will be based on LOCF. Summary of efficacy variables for the PP subjects will be based on available data. No imputation will be done for non-efficacy related variables.

If a partial date is reported where the day is missing, then the day will be imputed as the first day of the month unless the month is the same month as the first application of study drug then the day will be that of first application with the month and year remaining the same. If a partial date is reported where the month is missing, then the month will be imputed to January unless the year is the same year as the first application of study drug then the month will be that of first application with the year remaining the same. If a partial date where both the day and month is missing, follow details as stated previously.

Missing AE start dates will be imputed using partial date imputation rules as previously described in this Section.

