## **8. CHANGES IN THE PLANNED ANALYSES**

Baseline IGA will not be used as a factor for the primary, secondary, and exploratory efficacy IGA endpoints as treatment was not stratified by IGA score.

The ITT population was updated to specify inclusion only of subjects with at least one post-Baseline efficacy assessment.

The mITT population was added to the SAP in order to assess efficacy for subjects with consistent areas of AD lesions.

A tipping point analysis was added as an additional sensitivity analysis on the ITT population.

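### The primary ITT set leaves out randomised subjects with no post-Baseline efficacy assessment, and no planned efficacy analysis brings them back

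*SAP*

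**What the plan says.** Protocol 9.3.1 sets one condition beyond randomisation: "The ITT analysis set will consist of all randomized subjects with at least one post-baseline efficacy assessment". SAP 6.4.2 adds a second, so that subjects who "receive at least one application of study drug and have at least one post-Baseline efficacy assessment will be included in the ITT population". SAP 6.1 gives this set its weight: "The efficacy analysis performed on the ITT population is considered the primary analysis". For missing values, SAP 6.1.5 states that "the primary method of handling missing efficacy data in the ITT and mITT analysis set will be based on LOCF". Neither document scores a subject without data as a failure.

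SAP Section 8 describes the change this way: "The ITT population was updated to specify inclusion only of subjects with at least one post-Baseline efficacy assessment".

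Three other provisions bear on who ends up without an assessment:
- Protocol 6.3.8: if a subject "terminates the study early for reasons other than an AE, attempts will be made to complete the assessments required" for Day 85.
- SAP 6.1.3: "Data collected at early termination and unscheduled visits prior to study day 9 will not be analyzed", apart from values identified as Baseline.
- Protocol 4.3: "Subjects may be replaced after consultation with the sponsor".

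**The concern.** Membership of the primary set depends on something that happens after randomisation. The first scheduled post-Baseline efficacy visit is Day 15. A subject who leaves before any post-Baseline efficacy assessment is not counted as a failure; that subject is not counted at all. If the reason for leaving is related to treatment, through tolerability in one arm or lack of effect in the other, the two analysed groups are no longer the groups that were randomised. The trial exists to estimate response relative to vehicle, and that estimate is what would be distorted. The endpoint is binary, so a simple alternative exists that needs no new data.

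**Working it through.** **Plan's own figure.** The sample size is 100 + 100 = 200, set on clinical considerations (SAP Section 7). No success rate, effect, power or dropout rate is given, so the effect of exclusions can only be illustrated.

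**Does any planned efficacy analysis recover these subjects?**
- mITT and PP (SAP 6.4.3, 6.4.5) are subsets of ITT.
- The repeated-measures GEE and the tipping-point analysis (SAP 6.10) are both confined to ITT.
- The Randomized population (SAP 6.4.1) has listings and summaries, but no efficacy table uses it.
- Table 14.0.2 counts ITT exclusions by arm but does not analyse them.

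So none does.

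**Effect on the difference.** Let each arm have 100 randomised, with S_a and S_v successes and k_a and k_v subjects excluded. Excluded subjects have no observed success, so counting them as failures leaves S unchanged.
- All randomised: S_a/100 − S_v/100.
- Present ITT: S_a/(100 − k_a) − S_v/(100 − k_v).

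Assume S_a = 30 and S_v = 15:

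| Excluded (active, vehicle) | Calculation | Difference (points) |
|---|---|---|
| 0, 0 | 30/100 − 15/100 | 15.0 |
| 5, 5 | 30/95 − 15/95 = 31.6% − 15.8% | 15.8 |
| 8, 2 | 30/92 − 15/98 = 32.6% − 15.3% | 17.3 |
| 2, 8 | 30/98 − 15/92 = 30.6% − 16.3% | 14.3 |

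At these rates the active arm has twice the success rate, so vehicle must lose about twice as many subjects as active before the difference falls below 15.0. With 2 and 4 excluded, 30/98 − 15/96 = 30.61% − 15.63% = 14.99 points.

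**Effect on the test.** The test is the Wald test from a logistic regression with treatment only (SAP 6.8.1). With an assumed 31 and 19 successes:
- All randomised: 12.0 points, p = 0.052.
- 5 excluded per arm: 12.6 points, p = 0.050.
- 10 active and 2 vehicle excluded: 15.1 points, p = 0.021.
- 2 active and 10 vehicle excluded: 10.5 points, p = 0.105.

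**No true difference.** Take equal all-randomised success of 15%, 25% or 35%, with 10 active and 2 vehicle excluded. The spurious differences are:
- 15/90 − 15/98 = 1.4 points
- 25/90 − 25/98 = 2.3 points
- 35/90 − 35/98 = 3.2 points

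Two-sided type I error, by exact binomial enumeration, is 5.4%, 6.6% and 6.9%, against 4.5%, 4.9% and 4.8% with no exclusions. Reversing the imbalance reverses the sign of the bias. Equal losses give no bias in this case.

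**Early-termination assessments.** Protocol 6.3.8 limits the attempt to withdrawals not caused by an AE. The Protocol Summary (Methods), section 4.3 and footnote b of Table 4 call for Day 85 assessments after early withdrawal without that limit. The four places conflict.

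**Change record.** The post-Baseline condition is already in protocol 9.3.1. What SAP 6.4.2 adds is the requirement of at least one application, which Section 8 does not list.

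**The case against.** The strongest reply is that the effect is probably small and the tests are exploratory. Site staff apply the first dose on Day 1, at the visit where randomisation occurs, so the no-application condition should exclude almost nobody. The Phase 1b study of the same 4% product had no early discontinuations due to an AE, vehicle has the same excipients, and SAP 6.1.5 expects equal dropout. A reader could also divide the successes in Table 14.2.1.1 by the randomised totals. All of this limits the size. It does not remove the selection: the expectation of equal dropout has no figure behind it, and a hand calculation by the reader is not a planned analysis.

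Some stronger readings are tempting, but the documents do not support them:
- That AE dropouts go unassessed by rule and so always leave the set. Protocol 6.3.8 suggests it, but the other three places make no AE exception.
- That a visit before Day 9 removes a subject from ITT. SAP 6.1.3 says such early-termination and unscheduled data are not analysed; it does not mention membership, and SAP 6.4.2 sets no window. The case is unspecified.
- That replacement removes subjects. Nothing takes a replaced subject out of the randomised or ITT set.
- That the bias favours active. It can run either way.
- That all early dropouts vanish. From Day 9, early-termination data map to a visit and LOCF keeps the subject in.

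Two objections to the remedy also stand. Counting a subject as a failure gives no rule for continuous endpoints. It also scores the earliest dropouts as failures while later dropouts may still carry a success forward. The second is softened because eligible subjects have a Baseline IGA of 3, so carrying Baseline forward would give failure too.

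**Conclusion.** The concern holds for randomised subjects with no post-Baseline efficacy assessment. They are outside the primary IGA comparison and outside both sensitivity analyses. The status of a subject whose only assessment is an early-termination or unscheduled one before Day 9 is undefined.

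No figure in the documents is wrong as a result, and the size depends on losses that the documents do not predict. Under the assumed counts, an imbalance of 8 against 2 moves a 15.0-point difference by +2.3 or −0.7 points, depending on the arm that loses more; 5 lost from each arm adds 0.8. Since no confirmatory claim rests on the result, this is an inexpensive improvement to the estimate and does not threaten the trial. The Section 8 misdescription is real but changes no result.

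**What to change.** - For the primary and other binary IGA endpoints, analyse all randomised subjects by assigned arm. Count a subject with no analysable post-Baseline IGA as not achieving success, including one whose only assessment falls before Day 9.
- Extend the tipping-point analysis to all randomised subjects.
- Keep the present set, under another name, as a sensitivity analysis and for the continuous endpoints.
- In SAP Section 8, record the departure from protocol 9.3.1 and list the added condition of at least one application.
- Reconcile protocol 6.3.8 with the Protocol Summary, section 4.3 and Table 4 footnote b on early-termination assessments after an AE.

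No new data are needed. The costs are success rates that may read slightly lower, a primary set that departs from the one in the protocol, and a different set for binary IGA and continuous endpoints. The change goes beyond SAP wording, because the protocol carries the same post-Baseline condition and its early-termination text needs reconciling.

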#### **6.4.3 Modified Intent-to-Treat Population**

All subjects in the ITT population with no new areas of AD post-Baseline compared to Baseline BSA areas of AD will be included in the mITT population and analyzed according to the randomized treatment group. All efficacy analyses will be presented using the mITT population as supportive.

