5.1.2. Formulations, Appearance, Packaging, and Labeling

Botanix Pharmaceuticals' BTX 1204 contains the active pharmaceutical ingredient, cannabidiol (CBD). CBD is a member of a broader family of compounds known as cannabinoids, a class of compounds originally derived from the *cannabis sativa* plant. [Olah 2014] CBD is chemically synthesized under Good Manufacturing Practices (GMP) for use in this study.

BTX 1204 4% Liquid Formulation (active) is a clear to slightly yellow liquid solution with a 4% (w/w) concentration of CBD in a formulation of excipients, which have been used extensively in other topical products. These excipients include hexamethyldisiloxane, silicone gum, polypropylene glycol (PPG) 15 stearyl ether, and isopropyl alcohol (IPA). The solution spreads easily and quickly evaporates leaving the CBD on the skin.

Each milliliter of the BTX 1204 4% (w/w) Liquid Formulation contains 30.0 mg of CBD. The Vehicle will be identical to the BTX 1204 4% (w/w), but without the CBD.

Study drug, active and vehicle, will be supplied in 125 mL multi-dose, metered pumps delivering 0.5 mL per actuation. Each pump will contain approximately 100 mL of study drug. Each subject will apply up to 7 mL per dose. This will require 14 actuations of the pump. Each dose will cover all the subject's AD lesions (except scalp and groin).

Pumps for all groups will be labeled identically, except for kit number and bottle number, to maintain the blind.

Study drug will be applied directly to the AD lesion and spread to cover the AD lesion and up to 1 cm of the surrounding non-lesional skin. For lesions that cannot be accessed for direct application, study drug will be pumped into the palm of one hand and applied to the AD lesions.

Adequate study drug will be provided in kits for daily applications (BID) through 4 weeks (Day 28). Prior to distribution, pumps will be weighed by clinical site staff and the weights recorded in the source documents and the eCRF. When a subject is enrolled, the site will access the IWRS to receive a kit number for the first 28 days of dosing based on the IWRS randomization.

At the Day 29 and Day 57 Visits, the site will access the IWRS to obtain the kit number for the following 28 days of dosing. All distributed pumps will be returned by the subject at the Day 29, Day 57, and Day 85 Visits and weighed to monitor compliance and document doses delivered.

The study drug bottle may include the following information:

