APPENDIX A – CRITERIA OF HANNIFIN AND RAJKA

Hanifin and Rajka Diagnostic Criteria for Atopic Dermatitis (AD)

Major criteria: Must have three or more of:

1. Pruritus
2. Typical morphology and distribution
 - Flexural lichenification or linearity in adults
 - Facial and extensor involvement in infants and children
3. Chronic or chronically-relapsing dermatitis
4. Personal or family history of atopy (asthma, allergic rhinitis, atopic dermatitis)

Minor criteria: Should have three or more of:

1. Xerosis
2. Ichthyosis, palmar hyperlinearity, or keratosis pilaris
3. Immediate (type 1) skin-test reactivity
4. Raised serum IgE
5. Early age of onset
6. Tendency toward cutaneous infections (especially *S aureus* and herpes simplex) or impaired cell-mediated immunity
7. Tendency toward non-specific hand or foot dermatitis
8. Nipple eczema
9. Cheilitis
10. Recurrent conjunctivitis
11. Dennie-Morgan infraorbital fold
12. Keratoconus
13. Anterior subcapsular cataracts
14. Orbital darkening
15. Facial pallor or facial erythema
16. Pityriasis alba
17. Anterior neck folds
18. Itch when sweating
19. Intolerance to wool and lipid solvents
20. Perifollicular accentuation
21. Food intolerance
22. Course influenced by environmental or emotional factors
23. White dermographism or delayed blanch

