### **6.1.9 Use of an Efficacy Subset of Subjects**

One subset of interest is the mITT population. This subset is defined in order to better assess the effects of treatment on target areas; see Section 6.4.3 for definition.

Subjects randomized to study drug who complete the Day 85 visit without noteworthy study protocol violations, including compliance with study drug application, and completion of efficacy evaluations on Day 85 will form the PP population. Any noteworthy protocol violations will be defined at the time of evaluability evaluation, the time between the database soft lock and hard lock before unblinding.

Both mITT and PP analyses will allow for a further exploration of overall efficacy of BTX 1204.

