Number of Subjects Included in the ITT Population	xx ( xx.x%)	xx ( xx.x%)
Number of Subjects Excluded from the ITT Population	xx ( xx.x%)	xx ( xx.x%)
Reason for Exclusion from the ITT Population		
At Least One Post-Baseline Efficacy Assessment	xx ( xx.x%)	xx ( xx.x%)
Number of Subjects Included in the mITT Population	xx ( xx.x%)	xx ( xx.x%)
Number of Subjects Excluded from the mITT Population	xx ( xx.x%)	xx ( xx.x%)
Reason for Exclusion from the mITT Population a		
Not in the ITT Population	xx ( xx.x%)	xx ( xx.x%)
No New Post-Baseline Areas of Atopic Dermatitis b	xx ( xx.x%)	xx ( xx.x%)
Number of Subjects Included in the Safety Population	xx ( xx.x%)	xx ( xx.x%)
Number of Subjects Excluded from the Safety Population	xx ( xx.x%)	xx ( xx.x%)
Reason for Exclusion from the Safety Population a		
No Evidence of Subject Dosing	xx ( xx.x%)	xx ( xx.x%)
No Post Baseline Safety Assessment	xx ( xx.x%)	xx ( xx.x%)

a Table includes primary reason (assigned in order presented in table) subject was excluded.

b The presence of new areas of atopic dermatitis were determined by post-baseline reports compared to baseline reports of BSA.

c See Listing 16.2.3 for a complete list of all other reasons for exclusion from the PP population.

Note: The ITT exclusion of not being randomized is not presented as the table is on randomized subjects.

Percentages are based on the number of randomized subjects.

SOURCE: USERNAME/SPONSOR/PROJECT/JOBNAME (DATE,TIME)

Table 14.0.2: Summary of Subjects Excluded from Analyses  
(Randomized Subjects)  
(Page 2 of 2)

	BTX 1204 4% BID (N=xxx)	Vehicle BID (N=xxx)
Number of Subjects Included in the PP Population	xx ( xx.x%)	xx ( xx.x%)
Number of Subjects Excluded from the PP Population	xx ( xx.x%)	xx ( xx.x%)
Reason for Exclusion from the PP Population a		
Violated the Inclusion/Exclusion Criteria	xx ( xx.x%)	xx ( xx.x%)
Received an Interfering Medication	xx ( xx.x%)	xx ( xx.x%)
Missed Investigator Global Assessment at Day 85	xx ( xx.x%)	xx ( xx.x%)
Missed Both Day 29 and Day 57 Visits	xx ( xx.x%)	xx ( xx.x%)
Not Compliant with Dosing Regimen	xx ( xx.x%)	xx ( xx.x%)
Day 85 Visit not within +/- 7 days Window	xx ( xx.x%)	xx ( xx.x%)
Other c	xx ( xx.x%)	xx ( xx.x%)

a Table includes primary reason (assigned in order presented in table) subject was excluded.

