b The presence of new areas of atopic dermatitis were determined by post-baseline reports compared to baseline reports of BSA.

c See Listing 16.2.3 for a complete list of all other reasons for exclusion from the PP population.

Note: The ITT exclusion of not being randomized is not presented as the table is on randomized subjects.

Percentages are based on the number of randomized subjects.

SOURCE: USERNAME\SPONSOR\PROJECT\JOBNAME (DATE,TIME)

Table 14.0.3: Summary of Reasons for Screen Failure  
(Non-Randomized Subjects)

Reason for Screen Failure	Total (N=xx)
Adverse Event	xx ( xx.x%)
Inclusion and/or Exclusion Criteria	xx ( xx.x%)
Withdrawal by Subject	xx ( xx.x%)
Withdrawal by Legally Authorized Representative	xx ( xx.x%)
Lost to Follow-Up	xx ( xx.x%)
Other	xx ( xx.x%)

Note: Percentages are based on the number of non-randomized subjects.  
SOURCE: USERNAME\SPONSOR\PROJECT\JOBNAME (DATE,TIME)

Table 14.1.1.1: Summary of Subject Demographics  
(ITT Population)

	BTX 1204 4% BID (N=xxx)	Vehicle BID (N=xxx)
Age (years)		
n	xx	xx
Mean	xx.x	xx.x
SD	xx.xx	xx.xx
Median	xx.x	xx.x
Min., Max.	xx, xx	xx, xx
12 to < 18 Years	xx ( xx.x%)	xx ( xx.x%)
18 to < 30 Years	xx ( xx.x%)	xx ( xx.x%)
≥ 30 Years	xx ( xx.x%)	xx ( xx.x%)
Sex		
n	xx	xx
Male	xx ( xx.x%)	xx ( xx.x%)
Female	xx ( xx.x%)	xx ( xx.x%)
Ethnicity		
n	xx	xx
Hispanic or Latino	xx ( xx.x%)	xx ( xx.x%)
Not Hispanic or Latino	xx ( xx.x%)	xx ( xx.x%)
Race		
n	xx	xx
American Indian or Alaska Native	xx ( xx.x%)	xx ( xx.x%)
Asian	xx ( xx.x%)	xx ( xx.x%)
Black or African American	xx ( xx.x%)	xx ( xx.x%)
Native Hawaiian or Other Pacific Islander	xx ( xx.x%)	xx ( xx.x%)
White	xx ( xx.x%)	xx ( xx.x%)
Multiple/Other	xx ( xx.x%)	xx ( xx.x%)

Note: Percentages are based on the number of subjects in the ITT population with a non-missing response.  
SOURCE: USERNAME\SPONSOR\PROJECT\JOBNAME (DATE,TIME)

Repeat Table 14.1.1.1 for the following:

Table 14.1.1.2: Summary of Subject Demographics (mITT Population)

**Programming note:** *Replace footnote with* - Note: Percentages are based on the number of subjects in the mITT population with a non-missing response.

Table 14.1.1.3: Summary of Subject Demographics (PP Population)

**Programming note:** *Replace footnote with* - Note: Percentages are based on the number of subjects in the PP population with a non-missing response.

Table 14.1.1.4: Summary of Subject Demographics (Safety Population)

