xxxxxx	xxxx	xxxxxxxx	xxxx-xx-xx (xx) xxxx-xx-xx (xx) xxxx-xx-xx (xx)	xx xx xx	xxxxxxxx xxxxxxxxxxx xx xxxxx x xxxxxxx xxxxxxxx xxxxxxxxxxx xx xxxxx x xxxxxxx xxxxxxxx xxxxxxxxxxx xx xxxxx x xxxxxxx
xxxxxx	xxxx	xxxxxxxx	xxxx-xx-xx (xx) xxxx-xx-xx (xx)	xx xx	xxxxxxx xx xxx xxx

 Day = (date - date of first dose + 1) for dates on or after first dose. Otherwise, Day = (date - date of first dose).  
SOURCE: USERNAME\SPONSOR\PROJECT\JOBNAME (DATE, TIME)

Listing 16.2.6.1: Investigator Global Assessment  
 Treatment Group  
 (Page xx of yy)

S: Subject	Visit	Date/Time	Result	Two Grade Reduction from Baseline	Two Grade Reduction from Baseline and Achieving Clear or Almost Clear	Evaluator Initials or Reason Not Done
S: xxxxxx A: xxxx E: xxxxxxxx	xxxxxxx	xxxx-xx-xxTxx:xx	x - xxxx			xxx
	xxxxxxx	xxxx-xx-xxTxx:xx	x - xxxxxx			xxx
	xxxxxx	xxxx-xx-xxTxx:xx	x - xxxxxxxx	xx	xx	xxx
	xxxxxx	xxxx-xx-xxTxx:xx	x - xxxx	xx	xx	xxx
	xxxxxx	xxxx-xx-xxTxx:xx	x - xxxx	xx	xx	xxx
	xxxxxx	xxxx-xx-xxTxx:xx	x - xxxxxx xxxxx	xx	xx	xxx
S: xxxxxx A: xxxx E: xxxxxxxx	xxxxxxx	xxxx-xx-xxTxx:xx	x - xxxxxxxx			xxx
	xxxxxxx	xxxx-xx-xxTxx:xx	x - xxxxxxxx			xxx
	xxxxxx	xxxx-xx-xxTxx:xx	x - xxxxxxxx	xx	xx	xxx
	xxxxxx	xxxx-xx-xxTxx:xx	x - xxxx	xx	xx	xxx
	xxxxxx		xxx xxxx			xxx xxxxxx xxx xx
						xxxxxxxxxx
	xxxxxx	xxxx-xx-xxTxx:xx	x - xxxx	xx	xx	xxx

SOURCE: USERNAME\SPONSOR\PROJECT\JOBNAME (DATE, TIME)

Listing 16.2.6.2: Body Surface Area Affected by Atopic Dermatis  
Treatment Group  
(Page xx of yy)

S: Subject	Visit	Date	Evaluator Initials	Location	Result	Change from Bsaeline	Reason Not Done
S: xxxxxxx A: xxxx E: xxxxxxx	xxxxxxxx	xxxx-xx-xx	xxx	Head and Neck	x.x%		
				Right Arm	x.x%		
				Left Arm	x.x%		
				Right Leg	x.x%		
				Left Leg	x.x%		
				Trunk Front	x.x%		
				Trunk Back	x.x%		
				Total Body Surface Area	x.x%		
	xxxxxxxx	xxxx-xx-xx	xxx	Head and Neck	x.x%		
				Right Arm	x.x%		
				Left Arm	x.x%		
				Right Leg	x.x%		
				Left Leg	x.x%		
				Trunk Front	x.x%		
				Trunk Back	x.x%		
				Total Body Surface Area	x.x%		
	xxxxxx	xxxx-xx-xx	xxx	Head and Neck	x.x%		
				Right Arm	x.x%		
				Left Arm	x.x%		
				Right Leg	x.x%		
				Left Leg	x.x%		
				Trunk Front	x.x%		
				Trunk Back	x.x%		
				Total Body Surface Area	x.x%	x.x	
	xxxxx	xxxx-xx-xx	xxx	Head and Neck	x.x%		
				Right Arm	x.x%		
				Left Arm	x.x%		
				Right Leg	x.x%		
				Left Leg	x.x%		
				Trunk Front	x.x%		
				Trunk Back	x.x%		
				Total Body Surface Area	x.x%	x.x	

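### The SAP's mITT set is selected on a post-randomisation outcome (new AD areas), so its treatment comparisons are open to selection bias and cannot support the ITT result

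*SAP*

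**What the plan says.** SAP 6.4.3 restricts mITT to "All subjects in the ITT population with no new areas of AD post-Baseline compared to Baseline BSA areas of AD". A footnote to Table 14.0.2 gives the method: "The presence of new areas of atopic dermatitis were determined by post-baseline reports compared to baseline reports of BSA". The SAP sets no time limit, no minimum size and no rule for a new area that later clears.

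Two reasons are given. SAP 6.1.9 says "This subset is defined in order to better assess the effects of treatment on target areas". SAP 8 adds that the set was introduced to look at efficacy in subjects whose lesion areas stay consistent.

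On its role, SAP 6.4.3 says "All efficacy analyses will be presented using the mITT population as supportive". ITT is primary (SAP 6.1). Subgroup analyses of the primary endpoint are planned in mITT and PP only (SAP 6.1.11; Tables 14.2.1.6 and 14.2.1.7).

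Three other parts of the plan bear on what a new area means:

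- Change in percent BSA is a secondary endpoint (SAP 5.1.2).
- The IGA rates the overall state of the lesions at the visit, and its notes use extent to settle indeterminate grades (Protocol 6.1, Table 2).
- Study drug is applied to all lesions apart from scalp and groin (Protocol 5.1.2).

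**The concern.** Membership of mITT is decided by what happens to the skin under treatment. A new area is disease activity during the trial, measured with the same BSA report that supplies a secondary endpoint. The mITT analysis of BSA change therefore screens subjects on post-Baseline BSA and then compares post-Baseline BSA. For the IGA the link is less direct but present. Randomisation protects the comparison of arms as randomised. It does not protect a comparison of those who stayed free of new areas.

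Two features of the rule add to this:

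- **It looks ahead.** A subject with IGA success at Day 29 and a new area at Day 57 leaves the Day 15 and Day 29 mITT analyses and the mITT time-to-success curve as well.
- **It depends on follow-up.** A completer is examined at four post-Baseline visits (Days 15, 29, 57 and 85). A subject lost after Day 15 is examined at one, is more likely to stay in the set, and has values carried forward (SAP 6.1.5).

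At stake is the use of mITT as corroboration. If BTX 1204 prevents spread, the rule preferentially removes vehicle subjects who did badly and so works against the drug. If new areas are commoner on active, it works in the drug's favour. One of the only two planned subgroup displays also rests on this set.

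**Working it through.** **Inputs.** There is no plan figure to reproduce: the sample size (100 per arm) rests on clinical considerations, and no success rate or new-area rate is stated. All rates below are assumptions.

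**Formula A (new-area subjects never succeed).** With ITT success rate s and new-area share q in an arm, mITT success = s / (1 - q).

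**Formula B (new-area subjects succeed at half the rate of the others).** If the others succeed at rate p, then s = p(1 - q) + 0.5pq, so p = s / (1 - 0.5q).

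| ITT active vs vehicle | New areas, active / vehicle | mITT under A | Difference under A | mITT under B | Difference under B |
|---|---|---|---|---|---|
| 30% vs 20% (+10) | 30% / 30% | 0.30/0.70 = 42.9% vs 0.20/0.70 = 28.6% | +14.3 | 0.30/0.85 = 35.3% vs 0.20/0.85 = 23.5% | +11.8 |
| 30% vs 20% (+10) | 20% / 40% | 0.30/0.80 = 37.5% vs 0.20/0.60 = 33.3% | +4.2 | 0.30/0.90 = 33.3% vs 0.20/0.80 = 25.0% | +8.3 |
| 25% vs 25% (0) | 20% / 40% | 0.25/0.80 = 31.2% vs 0.25/0.60 = 41.7% | -10.4 | 0.25/0.90 = 27.8% vs 0.25/0.80 = 31.2% | -3.5 |

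**Range.** Take ITT 25% vs 15% (+10) under A, with new-area rates from 10% to 40% in each arm. The mITT difference runs from 25/90 - 15/60 = 27.8% - 25.0% = +2.8 to 25/60 - 15/90 = 41.7% - 16.7% = +25.0.

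**When the sign changes.** Under A, mITT favours vehicle only if sT/sV < (1 - qT)/(1 - qV).

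- With 18% vs 15% and new areas 10%/30%, 18/15 = 1.20 is below 0.90/0.70 = 1.29. mITT gives 18/90 = 20.0% vs 15/70 = 21.4%, so +3.0 becomes -1.4.
- If one new-area subject per arm is a success, mITT gives 17/90 = 18.9% vs 14/70 = 20.0%, or -1.1.
- With 25% vs 15%, the ratio is 1.67. The largest right-hand side in the 10-40% range is 0.90/0.60 = 1.50, so no reversal occurs.

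**Error rate.** In 200,000 simulated trials per scenario (100 per arm, true ITT success 20% in both arms, Formula A, pooled two-sided z test at 0.05), mITT rejected in 5.0% of trials with new areas 20%/20%, 15.4% with 10%/30%, and 33.0% with 10%/40%. ITT stayed at about 5% throughout.

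**The case against.** The strongest reply is that ITT is primary, mITT is labelled supportive, all tests are exploratory with no Type I error control, and SAP 8 discloses the addition. That stands, and it limits the weight of the point. It does not make mITT usable as support: every efficacy endpoint is repeated there, several with p-values, and nothing in the SAP acknowledges the selection or plans a check on it.

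Several stronger readings are tempting, but the documents do not support them.

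- **That mITT fails its own aim because its scores are whole-body.** In a subject with no new areas, whole-body IGA, Signs and BSA rate only the Baseline areas, and the second aim in SAP 8 is met by construction. The fault is selection.
- **That mITT would reverse a real effect.** This needs a small effect and unequal new-area rates. The third row of the table is bias away from a null, not a reversal.
- **That equal spread always inflates the difference.** It does so only if new-area subjects succeed less often. Even when none succeed, 30% vs 20% with 30% excluded per arm keeps the risk ratio at 1.50, and the odds ratio moves only from (0.30/0.70)/(0.20/0.80) = 1.71 to (0.429/0.571)/(0.286/0.714) = 1.88. It would also be too strong to call mITT results uninformative in every case.
- **That new-area subjects are mostly IGA failures.** This is assumed. The IGA is scored at the visit, so an area seen at Day 15 that later clears does not rule out success at Day 85.
- **That the protocol says relapse is expected in these subjects.** "Chronic or chronically-relapsing dermatitis" is one of four major diagnostic criteria, of which three are needed, and eligibility requires stable AD.
- **That every new lesion excludes a subject.** "Listing 16.2.6.2: Body Surface Area Affected by Atopic Dermatis" records seven body regions. If new areas are judged by region, a new lesion in an already affected region excludes nobody, and the SAP does not settle this.
- **That Table 14.0.2 shows the set is built backwards.** Its exclusion reason, "No New Post-Baseline Areas of Atopic Dermatitis", states the criterion rather than its failure. The ITT row does the same, so this is only labelling.

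**Conclusion.** The point holds as a limit on what mITT can be used for. Its membership rule is a post-randomisation outcome related to the BSA and IGA endpoints, so its treatment comparisons are open to selection bias and cannot serve as supportive evidence for the ITT result.

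The structural argument comes from the documents. The size does not. Under assumed rates, a 10-point ITT difference moves to +14.3 or +4.2 if new-area subjects never succeed, and to +11.8 or +8.3 if they succeed at half the rate of the others. A null moves to -10.4 or -3.5. The bias under a null needs unequal new-area rates, which is what a drug that affects spread would produce. The primary ITT analysis is not affected.

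**What to change.** Four changes to the SAP:

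1. Remove mITT as a set for treatment comparisons, or keep it as descriptive only, without p-values (SAP 6.1, 6.1.9, 6.4.3, 6.8).
2. In ITT, report by arm the proportion with a new AD area at any visit, as an outcome. State how a new area is determined, including whether by region.
3. Move the subgroup analyses of the primary endpoint (SAP 6.1.11, Table 14.2.1.6) to ITT. If mITT were simply deleted, they would remain in PP alone.
4. For the question about areas affected at Baseline, analyse in all ITT subjects the BSA summed over the regions affected at Baseline, using the seven-region data in Listing 16.2.6.2. State that this cannot separate new lesions within an already affected region, and that it answers the question for BSA only.

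**Cost.** SAP wording and table shells. Of the 15 mITT efficacy tables, one (subgroups) moves to ITT, and the other 14 and the mITT Kaplan-Meier figure are dropped or made descriptive. Two short tables are added from data already planned for collection. The downside is that the sponsor loses inferential use of a set it chose to add.
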